7.1 Screening

Potential study participants from each healthcare system followed in primary care clinics randomized to the study will be screened for inclusion according to the pre-established criteria for CKD, diabetes and hypertension (see section 5.1) and as illustrated in figure 6.3.1

There are no plans to obtain individual informed consent for patients screened or randomized in the study. (see section 14.3) Information about the study will be available to all patients in participating clinics and who have the triad of CKD, diabetes and hypertension. There will be an opt-out opportunity from the interventions or from use of information from any patient who requests their data not to be used for analysis.

Screening of participants will occur at an initial stage to identify a candidate cohort of patients in various eligible clinics (see figure 6.3.2). Patients who do not fulfill required diagnostic criteria on initial review and require a separate determination to confirm any of the three diagnosis will be rescreened at the time of a future visit (figure 6.3.3)

7.2 Enrollment/Baseline

Primary care practitioners will receive advanced notice (electronic and/or patient list) of eligible patients for the intervention group prior to their initial visit (visit 1). That visit will mark the first opportunity for initiation of the study by the primary care practitioner and to activate study interventions (see figure 6.4.1). The primary care practitioner will have the option of activating the study protocol and following recommendations using study tools/available smart forms.

7.3 Follow up Visits

Measures of blood pressure, blood glucose, kidney function (creatinine, eGFR), lipid levels, urine protein/urine albumin as well as pre-specified safety events will be captured from electronic health records at the time of patient contacts with the healthcare system for scheduled or unexpected visits for patients. Information will be then directed to primary care teams per study protocol.

Main study outcomes will be captured throughout the study for both intervention and control groups using the same tools in the electronic health record and access to DFW Regional Hospital Council, ProHealth database and VA electronic information systems.

The study does not specify the frequency of visits for study participants. It is anticipated that patients with the triad of CKD, diabetes and hypertension will usually be seen at a minimum of every 3-6months in most participating clinics.

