All eligible patients of practices who are randomized to the study will be included in the comparison of the two intervention groups regardless of intervention compliance (intention-to-treat analysis) to investigate if patients in intervention group have significantly less all-cause hospitalizations than those in the standard medical care group. Evaluation will also be performed to determine treatment effects on disease-specific hospitalizations, ER visits, cardiovascular events and deaths.

There will be two study groups: active intervention group randomized to the collaborative model of care facilitated by novel information technology and practice facilitators and standard/usual care group.

The total number of patients to be studied is 10,991. (see *study table 4*)

Healthcare System	Number of Practices	Number Patients to be Enrolled
Parkland Healthcare Systems	25	3,367
Texas Health Resources	40	3,610
ProHealth Connecticut	50	3,181
North Texas VA	9	833

Table 4
Study recruitment will occur over a period of two years. The expected duration of subject participation is 12 months.

The intervention in the active group is implementation of a collaborative model of care that facilitates delivering best care practices to patients who have coexistent CKD, type 2 diabetes and hypertension. The model uses a novel information technology platform and practice facilitators with the purpose of allowing for early identification of patients with objective criteria and to implement best practices of care, monitor important clinical measures, adjust treatments and achieve improved outcomes. The intervention will be delivered in the outpatient setting.

The primary outcome measured during the trial is 12-month all-cause hospitalization rate for all the study participants. Secondary outcomes measured during the trial include 30-day disease-specific readmissions (for all patients with an index hospitalization), emergency room visits, cardiovascular event, deaths and disease-specific hospitalizations.

Other secondary outcomes measured in the study include adverse safety events, episodes of acute kidney injury and changes in estimated GFR.

Data collection for assessment of study objectives will be mainly based on information technology tools to capture data from the electronic health record. Some data fields will require collection of data from Dallas Fort Worth Regional Hospital Council, ProHealth ACO databases, VA of North Texas and Social Security Death Files Index.

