7.4 Final Study Visit

The final study visit will be the patient visit closest to 12 months after initiation of the study for that patient. As previously stated, visits will be for ongoing care and not mandated for study/research interventions.

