9.1 Specification of Safety Parameters

Adverse safety events will be captured and monitored as part of the study. The primary outcome of this trial is all-cause hospitalizations for patients with a triad of CKD, diabetes and hypertension and all unplanned hospitalizations will be captured. The main secondary outcomes that will be captured in the study also include safety events including 30-day all cause readmissions (for those patients who have an index hospitalization), emergency room visits, cardiovascular events, deaths, and disease-specific hospitalizations. In this study disease-specific hospitalizations include all those hospitalizations for cardiovascular complications, congestive heart failure, volume overload, hypertension complications, acute coronary syndrome, myocardial infarction, coronary/peripheral revascularization, stroke, amputation/limb ischemia, uncontrolled diabetes, hypoglycemia, diabetes complications, acute kidney injury, hyperkalemia, electrolyte disturbances, medication errors, drug toxicity, and infections.

In this study the control group will receive standard of care. The intervention group will receive interventions that are already accepted as best practices. Primary care providers will make ultimate decisions regarding implementation of any of the interventions for both groups. In addition to the study outcome measures detailed above the following events will be captured and reported (whether they lead to hospitalizations or not) as they could be related to potential study interventions: hypotension, syncope, hyperkalemia, electrolyte disturbances, angioedema, hypoglycemia, rhabdomyolysis, myositis, drug toxicity, pregnancy while treated with ACEI or ARB, acute kidney injury, reductions in eGFR 50% or higher, or initiation of dialysis.

The study will monitor for any malfunctions on the decision support software system and SFTP used for data transmission to and from electronic health records of the study sites for Parkland, THR, ProHealth and VA of North Texas. There will also be monitoring for adherence to Manual of Procedure interventions including identification and enrollment of eligible patients, activation of study protocols and recommended follow up.

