- a If patient is already on ACEi or ARB but not at maximum tolerated dose (see above), increase dose to achieve SBP and DBP goal (as per ACEi/ARB PROTOCOL below)
- b If patient is on maximum tolerated dose of ACEi or ARB, proceed to NON ACEi/ARB PROTOCOL.
- c If patient is not on ACEi or ARB, confirm allergies with patient.
- d If no prior allergy or adverse reaction to ACEi or ARB, proceed to ACEi/ARB PROTOCOL.
- e If prior allergy to ACEi is cough, proceed to ACEi/ARB PROTOCOL.
- f If prior allergy or adverse reaction to ACEi or ARB other than cough, consult with provider safety of starting ACEi or ARB.
- g If after discussion with provider, ACEi and ARB are both considered contraindicated, update allergies as needed

and proceed to NON-ACEi/ARB PROTOCOL.

ACEi/ARB PROTOCOL

1. Consider this protocol active until completed.
2. Review "Results Review" for past potassium and creatinine (abbreviated as "Cr" and "K" respectively hereafter). If both are available, no further action is needed. If one or both is not available in last 3 months, order both CREATININE LEVEL and POTASSIUM LEVEL as appropriate (referred to as "Cr/K Check" hereafter).
 - a. Lab Results Interpretation
 - i. Is K > 4.9?
 1. Yes
 - a. Discuss with provider before starting or increasing ACEi or ARB.
 2. No
 - a. If not on ACEi/ARB, and no prior allergy to ACEi or ARB, route pended order to provider for lisinopril 5mg once daily and proceed to "Follow-Up" below.
 - b. If not on ACEi or ARB and prior cough due to ACEi but no other ACEi or ARB allergy, route pended order to provider for losartan 25mg once daily and proceed to "Follow-Up" below.
 - c. If already on ACEi or ARB, but not at maximum tolerated dose, increase dose and proceed to "Follow-Up" below.
 - d. If already on ACEi/ARB at maximum tolerated dose, consider this protocol COMPLETED and proceed to NON-ACEi/ARB PROTOCOL.
 - e. Follow-Up
 - f. Schedule RN BP Assessment Visit and Cr/K Check 1-3 weeks following initiation or dose increase. Request patient to have labs drawn prior to appointment.
 - b. K Interpretation
 - i. Is K > 5.4?
 1. Yes. Discuss with provider stopping ACEi/ARB
 2. No
 - ii. 1. Is K > 4.9?
 3. Yes
 - a. Continue ACEi/ARB at current dose.
 - b. Provide patient with low potassium diet handout
 - c. Order repeat POTASSIUM LEVEL in 1 week.
 - d. If K is not < 5.0 on repeat evaluation, discuss with provider.
 - e. If K is </= 4.9, proceed to Cr Interpretation.
 4. No - proceed to Cr Interpretation.

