
- a. Schedule RN BP Assessment Visit in 2-4 weeks
- b. Order POTASSIUM LEVEL and CREATININE WITH E-GFR and request patient have labs drawn at least 1 business day prior to visit.
- c. Perform RN BP Assessment as detailed above in 2-4 weeks.
- d. Is K > 3.4?
 - i. No. Discuss with provider change in therapy or potassium supplementation. Discuss follow up plan for K with provider as well.
 - ii. Yes
 - 1. Is GFR > 10% lower than last value?
 - a Yes. Discuss with provider decrease in diuretic dose or stopping diuretic. Discuss follow up plan for Cr with provider as well.
 - b No. Is BP at goal?
 - (i) If BP is still not at goal at maximum tolerated dose of diuretic, return to NON-ACEi/ARB PROTOCOL.
 - (ii) If BP is still not at goal and not taking chlorthalidone 25mg or maximum tolerated dose of diuretic, then discuss with provider if dose of diuretic should be increased.
 - (iii) If provider recommends to increase dose, schedule for "Follow-Up" as detailed above in 2-4 weeks.
 - (iv) If provider recommends to not increase dose, return to NON-ACEi/ARB PROTOCOL.

CALCIUM CHANNEL BLOCKER PROTOCOL

1. Discuss following medication suggestions with provider. These are only suggestions to guide management, but final selection is at provider's discretion.
2. Perform RN BP Assessment as detailed above.
3. Is BP at goal?
 - a. Yes. Continue regimen and schedule RN BP Assessment Visit in 3 months and follow-up with PCP within 6 months.
 - i. If BP continues to be at goal in 3 months, can return hypertension management to PCP.
 - b. No. Is patient already taking calcium channel blocker (CCB)?
 - i. Yes - Is CCB at maximum dose?
 - 1 Yes. Return to NON-ACEi/ARB PROTOCOL.
 - 2 No. Route pended order to provider for double dose of current CCB and schedule for "Follow-Up" as detailed below in 2-4 weeks.
 - a No. Does patient have proteinuria as defined above?
 - b Yes. Route pended order for verapamil SR 120mg once daily and

proceed to "Follow-Up" below.

c No. Route pended order for amlodipine 5mg once daily and schedule for "Follow-Up" as detailed below in 2-4 weeks.

4. Follow-Up

- Perform RN BP Assessment as detailed above in 2-4 weeks.
- Is HR ≥ 100 ?
 - Yes - discuss with provider
 - No. Is BP at goal?
 - Yes. Continue regimen and schedule RN BP Assessment Visit in 3 months and follow-up with PCP within 6 months.
 - If BP continues to be at goal in 3 months, can return hypertension management to PCP.
 - No. Is CCB at maximum dose?

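### Outpatient kidney, potassium and blood-pressure safety events are counted at whatever contacts occur, and Appendix I adds contacts and blood draws in the intervention arm only, so by-arm counts partly measure testing intensity

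*Combined protocol and SAP*

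**What the plan says.** **Capture.** Section 7.3 (Follow up Visits) states that pre-specified safety events, blood pressure, creatinine and eGFR "will be captured from electronic health records at the time of patient contacts with the healthcare system for scheduled or unexpected visits for patients". It adds that "The study does not specify the frequency of visits for study participants" and expects that patients "will usually be seen at a minimum of every 3-6months in most participating clinics". Section 7.4 says that "visits will be for ongoing care and not mandated for study/research interventions".

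**What counts.** Section 9.1 states that "the following events will be captured and reported (whether they lead to hospitalizations or not"; its list includes hypotension, hyperkalaemia, electrolyte disturbances, AKI and eGFR reductions of 50% or more. Section 4 (Study Design) adds: "Other secondary outcomes measured in the study include adverse safety events, episodes of acute kidney injury and changes in estimated GFR". Section 3.2.2 lists the same kidney measures among the other secondary outcomes.

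**What the intervention adds.** Section 6.5 places the appendix protocols inside the collaborative model, for activation at the practitioner's option. Once Appendix I is active:

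- Its ACEi/ARB section says: "Schedule RN BP Assessment Visit and Cr/K Check 1-3 weeks following initiation or dose increase". A potassium above its threshold leads to a repeat level after one week.
- Its diuretic follow-up says: "Order POTASSIUM LEVEL and CREATININE WITH E-GFR and request patient have labs drawn at least 1 business day prior to visit".
- Its pre-visit planning orders creatinine and potassium when none are recent.
- Nurses measure blood pressure and are told to ask about adverse effects, including lightheadedness and fainting, at every visit.

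No matching schedule is set for control practices.

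**How the events are used.** Section 9.2.4 starts a case review and a report to the DSMB when safety events trend upward in the intervention group. Section 2.3 describes quarterly DSMB reporting of these events for the intervention group. Section 11.3 gives no analysis rule for outpatient laboratory events.

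**The concern.** A transient potassium rise, creatinine rise or low blood pressure enters the record only if someone measures it. If one arm is measured more often because of its allocation, more of its patients will show at least one event even when true risk is the same. Section 7.3 promises the same electronic tools in both arms for the main outcomes. That equalises extraction, not how often a patient is tested. Section 6.7 will compare utilisation between arms but does not link it to event detection.

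At stake are the interpretation of listed secondary and safety outcomes and of the section 9.2.4 trigger. A real effect of the drugs on potassium or creatinine would push in the same direction, and the plan as written cannot separate it from extra detection.

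**Working it through.** The plan gives no figure for test frequency or outpatient event rates, so there is none to reproduce. Its sample size of 10,991 concerns the primary outcome and is not at issue here.

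**Inputs from the documents**

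- Background contacts: every 3 to 6 months (section 7.3), so 12/6 = 2 to 12/3 = 4 a year. One panel per contact is assumed.
- ACEi steps in Appendix I: lisinopril starts at 5 mg and is doubled to a maximum of 40 mg. The sequence 5, 10, 20, 40 is one start and three increases, so up to 4 creatinine/potassium checks.
- Diuretic steps: chlorthalidone from 12.5 to 25 mg is one start and one increase, so up to 2 more checks.
- Together, up to 4 + 2 = 6 extra panels for a fully titrated patient. Repeat potassium levels and pre-visit labs are left out.

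**Assumptions, not in the documents**

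- The same chance q of a flagged result per panel in both arms, varied from 0.5% to 5%.
- Uptake u of Appendix I among intervention patients.
- Within-patient correlation r of 0 or 0.3.

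**Formulas**

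- Independent panels: P(k) = 1 − (1 − q)^k.
- Correlated panels (beta-binomial): P(k) = 1 − Γ(b+k)Γ(a+b) / [Γ(b)Γ(a+b+k)], with a = q(1−r)/r and b = (1−q)(1−r)/r.
- Intervention arm with e extra panels: u·P(k+e) + (1−u)·P(k).

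**Results under equal true risk**

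| q | Panels, control v intervention | Uptake | r | Control | Intervention | Ratio |
|---|---|---|---|---|---|---|
| 1% | 2 v 8 | 100% | 0 | 2.0% | 7.7% | 3.9 |
| 3% | 3 v 9 | 100% | 0 | 8.7% | 24.0% | 2.7 |
| 3% | 3 v 6 | 100% | 0 | 8.7% | 16.7% | 1.9 |
| 3% | 3 v 6 | 50% | 0 | 8.7% | 12.7% | 1.5 |
| 3% | 3 v 6 | 25% | 0 | 8.7% | 10.7% | 1.2 |
| 4% | 4 v 5 | 100% | 0 | 15.1% | 18.5% | 1.2 |
| 1% | 2 v 6 | 100% | 0.3 | 1.7% | 3.3% | 2.0 |
| 1% | 4 v 8 | 25% | 0.3 | 2.65% | 2.94% | 1.1 |

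Worked example for 25% uptake: 1 − 0.97³ = 0.0873 and 1 − 0.97⁶ = 0.1670. The intervention arm is 0.25 × 0.1670 + 0.75 × 0.0873 = 0.1073, and 0.1073/0.0873 = 1.2.

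With 3 to 6 extra independent panels for every patient, 2 to 4 control panels and q of 1% to 5%, the ratio runs from 1.6 to 3.9. Partial uptake, correlation or a single extra test brings it down to 1.1 to 1.2. Whenever the intervention arm is tested more, the ratio exceeds 1.

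**The case against.** The case on the other side has several parts, most of which limit the scope.

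- **Appendix I is not mandatory.** Sections 6.5 and 7.2 make activation optional, the appendix allows deviations, its non-ACEi/ARB steps are suggestions, and blood pressure at goal needs no further action. It refers to Parkland's own pharmacy, and Parkland supplies 3,367 of 10,991 patients (31%), so equal use in all four systems is not shown. In the uncontrolled pilot (section 2.2.3, n=107), 57.8% already met the ACEi/ARB goal at screening. All this stands. The same pilot reports 87.2% at last follow-up, so added starts are plausible.
- **Control patients may be tested too.** Table 7.1 lists laboratories at every visit without distinguishing arms. Section 7.4 leaves those visits unmandated, so the table does not secure equal testing.
- **No biased test is specified.** Section 11.3 names no between-arm test of outpatient AKI, potassium or electrolyte events. Hospitalised AKI, hyperkalaemia and electrolyte disturbance are already components of disease-specific hospitalisation, which it does compare. This stands.
- **A change in eGFR does not rise mechanically with the number of tests**, and section 7.4 already defines a final visit closest to 12 months. This stands. The detection problem applies to the 50% fall as an event; for eGFR change, what is missing is a stated common window.
- **Review precedes any halt.** Section 9.2.4 leads first to case review, sections 9.2.1 and 9.2.2 add relatedness and chart review, and halting under section 9.5 is discretionary. A reader might infer that extra testing would stop the trial; the documents do not support that.

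**Conclusion.** The mechanism is documented at each step and nothing in the plan corrects for it. By-arm counts of outpatient AKI, hyperkalaemia, electrolyte disturbance, hypotension and eGFR falls of 50% or more will partly reflect how often patients are tested, with a lean toward apparent harm in the intervention arm. That direction rests on Appendix I producing net extra testing there. The size cannot be fixed from the documents: 1.1 to 3.9 is an illustration under equal true risk, and its top end assumes six extra independent panels in every patient.

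Two stronger readings might be inferred and are not supported. One is that the excess must be at least 1.6-fold, which requires at least three extra independent panels for every patient. The other is that the primary comparison is compromised, whereas all-cause unplanned hospitalisation does not directly depend on outpatient laboratory frequency. This should be changed, but it does not threaten the main result.

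**What to change.** Amend sections 3.2.2, 9.1 and 11.3 as follows.

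1. Beside every table of outpatient safety events, including those for the DSMB, report creatinine tests, potassium tests and contacts per patient-year for both arms. Reconcile section 2.3, which names the intervention group only, with section 9.1, which has no such limit.
2. For AKI, hyperkalaemia, electrolyte disturbance and hypotension, make events identified at an emergency visit or hospitalisation the main between-arm comparison, extending the existing disease-specific hospitalisation analysis. Keep all outpatient laboratory events as descriptive safety data so that real drug effects stay visible.
3. Compare eGFR change using one baseline value and the one value nearest month 12 in the same fixed window in both arms, for example months 9 to 15. Use all draws in the window. Excluding Appendix I draws would delete data from one arm only.

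The cost is wording and some tabulation from data already extracted. No visits, draws or treatment rules change. The main comparison will have fewer events. It is also not wholly free of the problem, because an abnormal protocol result prompts a discussion with the provider that could lead to referral.

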7.4 Final Study Visit

The final study visit will be the patient visit closest to 12 months after initiation of the study for that patient. As previously stated, visits will be for ongoing care and not mandated for study/research interventions.

7.5 Unscheduled Visits

Acquisition of data/facilitation of care at the time of unscheduled visits will follow the schedule described in section 7.3. This is, however, an outpatient study. There will be capture of relevant data from hospitalizations (including major outcome measures) but study interventions and application of study tools will not be actively implemented during hospitalizations.

7.6 Early Termination Visits

Patients and/or primary care practitioners may decide at any time to discontinue participation in the facilitated collaborative model of care. Outcomes will still be captured for intention-to-treat analysis unless participants request their data/information not to be used. Table 7.1 summarizes the visits in the study.

Schedule of Events		Prior to Visit 1	Visit 1/Baseline	Visit 2 (3 months)	Visit 2 (6 months)	Visit 4 (9 months)	Visit 5 (12 months)	Study Completion
Assessment of Eligibility (Screening)		X						
Enrollment			X	X	X	X	X	
Medical History			X	X	X	X	X	
Medication Review			X	X	X	X	X	
Physical Exam (BP)			X	X	X	X	X	
Laboratories			X	X	X	X	X	
Surveys	HRQOL		X					X
	Practitioner Satisfaction		X					X
Education/Counseling			X		X			

*Most patients are usually seen every 3-6 months although more frequent visits occur in some patients based on treatments/clinical volume

Table 7.1 Schedule of Visits/Events

8. Study Procedures/Evaluations

8.1 Clinical Evaluations

The study does not mandate interventions or evaluations considered experimental or outside of those recommended as part of optimal evidence-based care for patients with CKD, diabetes and hypertension.

- Medical history and emphasis on problem list and diagnostic codes.
- Medications including lists of all medications from electronic health record and medication reconciliation
- Physical examination with special emphasis to blood pressure readings.
- Education/counseling procedures. There will be emphasis on lifestyle modifications and confirmation of immunizations and interventions related to healthcare interventions. This will also be an opportunity to insure distribution of education on chronic kidney disease and diabetes. See information from NKDEP.^[82]
- Criteria for dose adjustment. Recommended goals for clinical measures and suggestions for recommendations are included in the specific protocols for CKD, hypertension, dyslipidemia, lipid management and diabetes management. (see appendix)]

